1.5. Aspirin’s Secondary Role – Prevention of new polyps

There is currently high quality evidence from a series of prospective placebo-controlled randomized studies that Aspirin and NSAIDs reduced the incidence of colorectal adenomas (table 7). Therefore since patients with resected colorectal cancer are at increased risk of developing a second metachronous cancer (up to 3% of patients in the first 5 years), they may derive secondary benefit from the use of aspirin.

In the study by Sandler et al, a total of 635 patients were randomised to receive Aspirin 325 mg daily or placebo. One or more adenomas were found in 17% of patients in the Aspirin group and 27 % of patients in the placebo group (P=0.004). The relative risk of any polyp in the Aspirin group was 0.65 (95%CI 0.46-0.91) and the time to detect the first adenoma was longer in the Aspirin group than in the placebo group.³⁵ In the Baron study, patients were randomised to receive Aspirin at 81 mg, 325 mg or placebo. For advanced neoplasm (adenomas measuring at least 1 cm, or with villous, tubulovillous features, severe dysplasia or invasive cancer) the relative risks were 0.59 (95% CI 0.38-0.92) for the 81 mg arm and 0.83 for the 325 mg Aspirin arm.³⁶ In a third trial by Logan et al, 945 patients were randomised to Aspirin, Folate supplementation or placebo. Whereas no benefit was found for folate, Patients on Aspirin had a significant reduction in polyp burden.³⁷ More recently, a 375 patient randomised study demonstrated that patients treated with Sulindac and Difluoromethylornithine (DMFO), a drug also used to treat trypanosomiasis, reduced the risk of recurrent adenomas by 72% and high risk adenomas by 92%.³⁸ This magnitude of reduction was much larger than expected and in fact was the greatest seen for any chemoprevention trial to date and this has sparked off a renewed interest in the use of NSAID combination agents for chemoprevention.³⁹ Cox2 inhibitors studies (i.e. APC, PreSAP, APPROVe) have also shown this class of agents to be effective in reducing polyps,⁴⁰⁻⁴² however their adverse cardiovascular profile precludes their long term use for this indication. Aspirin however is cardio-protective and can be safely administered over prolonged periods of time.⁴³⁻

Study / Author	No of Subjects	Intervention	Results	Reference
Baron et al	1121	Aspirin 81mg vs Aspirin 325mg vs Placebo	RR 0.59 for high risk polyps in 81mg Aspirin arm	N Engl J Med 2003;348:891
Sandler et al	517	Aspirin vs Placebo	RR 0.65 for any adenoma in 325mg Aspirin arm.	N Engl J Med 2003;348:883
Logan et al	945	Aspirin 300mg Vs Folate 0.5mg Vs Placebo	RR 0.79 for any adenoma and 0.63 for high risk adenoma in Aspirin arm	Gastroenterology 2008; 134:29
Meyskens et al	375	Sulindac + DMFO Vs Placebo	RR 0.3 for any adenoma and RR 0.085 for high risk adenoma	Cancer Prev Res 2008;1:32
APC study	1364	Celecoxib vs Placebo	RR 0.67 for 200mg bd dose and RR 0.55 for 400mg bd dose	N Engl J Med. 2006;355:873
PreSAP study	1561	Celecoxib vs Placebo	RR 0.64 for adenomas and RR 0.59 for high risk adenomas	N Engl J Med. 2006;355:885
APPROVe Study	2587	Rofecoxib vs Placebo	RR 0.76 for adenomas. RR 0.65 for advanced adenomas	Gastroenterology 2006;131:1674

Table 7. NSAIDs and Polyp prevention

1.6. Primary Prevention of Colorectal Cancer

A large number of epidemiological and clinical studies have shown a strikingly consistent 40 to 50 percent reduction in the risk of colorectal neoplasia, in patients on regular aspirin, despite the differences in study designs, populations, and patterns of Aspirin use.⁴⁵

In a retrospective Australian case control study performed in the 1980s, Kune et al noticed that there was a significant deficit of heart disease, stroke and arthritis in patients who had colon cancer who used regular aspirin amongst 715 colon cancer cases matched against 727 controls. On multivariate analysis, controlling for heart disease and stroke, the association between aspirin use and incidence of colon cancer persisted and remained highly significant across gender and disease site.⁴⁶

Later, in a prospective mortality study of 662,424 individuals who provided information on the frequency and duration of their aspirin use, Thun et al noted that death rates from colon cancer decrease with more frequent aspirin use. The relative risk among persons who used aspirin 16 or more times per month for at least one year was 0.60 in men (95% CI 0.40 - 0.89) and 0.58 in women (95% confidence interval, 0.37 - 0.90). Adjustment for dietary factors, obesity, physical activity, and family history did not alter the findings significantly and no association was found between the use of acetaminophen and the risk of colon cancer.⁴⁷

Further support comes from the analysis of the results of the National Health and Nutrition Examination Survey I (NHANES I) and the NHANES I Epidemiologic Follow-up Studies (NHEFS). Amongst 12 668 responding subjects who were followed up an average of 12.4 years, 1,257 were eventually diagnosed with cancer. The relative risk of colorectal cancer amongst younger men who were regular users of aspirin was 0.35 (95% CI 0.17-0.73).⁴⁸

In the Nurses Health Study, women were surveyed using 3 consecutive questionnaires in 1980, 1982 and 1984. Incidence of colorectal cancer in women who were consistent users of aspirin, defined as

ICR02 /ASCOLT

2 or more tablets a week, were compared with non-users. In total, 331 new cases of colorectal cancer diagnosed during 551,651 person-years of follow-up. Although there was no difference at 4 years; after 20 years of consistent aspirin use, there was a statistically significant reduction (relative risk, 0.56; 95% CI 0.36 to 0.90; P for trend = 0.008).⁴⁹.

More recently, a combined analysis of two randomised aspirin trials (The British Doctors Aspirin Trial and the UK-TIA Aspirin Trial), demonstrated that Aspirin reduced the incidence of colorectal cancer with a Odds Ratio (OR) of 0.74 (95% CI 0.56-.97). Subjects in these studies were randomised prospectively to aspirin or placebo, but with a vascular outcome as the primary endpoint. In compliant patients who received Aspirin for 5 years or more, the OR for incidence of new colorectal cancer at 10-14 years was 0.26 (95% CI 0.12-0.56, p=0.0002). A systemic review of published observational studies performed by the same authors showed that in 19 case-control studies (20,815 cases) and 11 cohort studies (1,136,110 individuals), regular use of Aspirin or NSAID was consistently associated with a reduced risk of colorectal cancer.⁵⁰

In the Women's Health Study, 39 876 women were randomised in a 2x2 factorial trial design to aspirin 100mg every other day, vitamin E and placebo. After an average 10 yrs of follow up, 2865 new cases of invasive cancers were diagnosed however there was no effect of Aspirin on the incidence of all cancers or colorectal cancer. This study was however limited by the low dose and (alternate-day) schedule of aspirin administration.⁵¹

Study / Author	Study Type	No of Subjects	Results	Reference
Kune et al.	Case-Control	715 colon cases vs 727 controls	significant deficit of colon cancer amongst aspirin users	Cancer Res 1988 ;48:4399
Thun et al.	Nested Case-Control	662,424	Death rate from gastrointestinal cancer 40% lower amongst individuals who used Aspirin 16 times/ mth or more.	Cancer Res 1993; 15; 53 (6): 1322-7
NHANES I and NHEFS study	Nested Case-Control	12,668	Lower incidence risk across several cancers with the lowest risk amongst young male aspirin users	Epidemiology 1994; 5(2):138-46
Nurses Health Study	Nested Case-Control	551,651 person yrs of follow up	Lower risk of colon cancer with prolonged aspirin use	N Engl J Med 1995; 333 : 609-14
US Physician Health Study	Randomised trial evaluating aspirin in vascular disease	22,071	No Benefit	N Engl J Med 1989; 321:129
Women's Health study	Randomised trial evaluating aspirin in vascular disease	39,876	No Benefit	JAMA 2005;294:47
Flossman et al	Randomised trials evaluating aspirin in vascular disease	7588	Overall lower incidence of colorectal cancer HR 0.74, (95% CI 0.56-0.97) in Aspirin users. Amongst compliant patients with prolonged (>5 yrs) use, HR 0.26 (95CI 0.12-0.56)	Lancet. 2007 May 12;369(9573):1603-13

Table 8. Aspirin and Primary prevention of colorectal cancer

1.7. Preclinical data and scientific rationale

The pathways and mechanisms in which aspirin/ NSAIDs inhibit colon cancer cell growth are multiple, and complex.^{52,53} Aspirin and Indomethacin have been shown in numerous animal studies to reduce the incidence, multiplicity and size of chemically induced gastrointestinal cancers⁵⁴⁻⁵⁶ and in APC min mice.⁵⁷ Aspirin has also been shown to have anti-angiogenic properties in vitro and is able to potently inhibit endothelial cell migration and endothelial capillary tube formation.⁵⁸ Sulindac and cox2 inhibitors have also been shown to reduce microvascular density, cell proliferation index and increase apoptosis in-vivo, in athymic xenograft mouse models.⁵⁹ Recently in an aggressive ovarian clear-cell cancer mouse model, mice treated with aspirin were noted to have markedly lower ascitic volume, smaller area of diaphragmatic tumor coverage, and a longer time to disease progression and distant metastasis.⁶⁰ Through a series of experiments, the authors were able to show that increased local and systemic inflammation always accompanied tumor progression and the extent of inflammation also corresponded with disease progression. By modulating inflammation via macrophage depletion, researchers were able to alter rate of cancer progression in the mice – thus demonstrating that aspirin's activity was dependent on the adaptive immune system. This is particularly interesting because inflammation stands at the nexus of the adaptive immune response, and the latter is an extremely powerful prognostic marker in human colon cancer.⁶¹

Whilst it is well known that chronic inflammation predisposes to certain malignancies, it has only recently recognized that a maladaptive inflammatory response is required for malignant transformation and metastasis.⁶² Indeed Hanahan and Weinberg have included tumor promoting inflammation as one of the key hallmarks of cancer.⁶³ Inflammation has been shown to induce widespread epigenetic changes in ileum of mice (i.e. methylation of polycomb target genes) leading to silencing of multiple genes required for the development of cancer.⁶⁴ Studies have also linked proinflammatory PGE2 (a downstream product of cox activation) with colon cancer carcinogenesis via complex interactions with stem cell pathways.^{65,66} Indeed mice which lack the ability to produce PGE2 have resistance to colon cancer.⁶⁷ The evidence from preclinical studies is also finding some support from several human studies. For example, a very large cohort study in China found a strong association between urine PGE2 and the risk of developing colon cancer⁶⁸ and another Scottish study, noted that high pre-operative CRP levels correlated with poor tumor specific survival.⁶⁹ Low doses of Aspirin has been shown to be highly effective in reduce rectal mucosal PGE2 levels in human subjects^{70,71} and this may be one reason to explain its anti-cancer effect.

Aspirin is a non-selective inhibitor of cox and binds to both cox-1 and cox-2 in an irreversible fashion. Whereas cox-1 is constitutively activated in all tissues, cox-2 represents an inducible isoform that is only expressed in inflamed tissues. Cox-2 is not normally expressed in normal colonic epithelial tissue, however it is over-expressed in 40-50% of adenomatous polyps and in 85% of colon cancers.⁷² Further, the intensity of cox over-expression is higher in metastasis when compared to the primary colonic tumor. Cox-2 has been shown to play an important role in tumor growth and studies of cox-2 knock-out mice have demonstrated inhibition of tumor growth versus wild type mice. Conversely, when wild type mice were treated with cox-2 inhibitors, it also demonstrated a similar ability to retard tumor growth.⁷³ It is currently believed that NSAIDs and cox-2 inhibitors also act on additional pathways apart from cox. Invitro studies in some instances seem to indicate NSAIDs do not require

the presence of cox-2 to prevent cancer and are able to demonstrate an ability to inhibit cell proliferation, angiogenesis and to induce apoptosis, even in the absence of cox-1 and/or cox-2.⁷⁴. Indeed, most recent analysis of colorectal cancer patients in the Nurses Health Study indicate that tumor PIK3CA mutational status may help select for patient who would benefit from aspirin treatment.⁷⁵

1.8. Optimal biologically effective dose for Aspirin

The optimal dose of Aspirin as an adjuvant agent for colorectal cancer is not known. There have been, to date, no randomised Aspirin trials exploring *secondary prevention* as an endpoint. Non-randomised studies evaluating Aspirin as a *primary prevention* agent have suggested that a dose of 300 mg a day for 5 years is effective^{31,50}. In the analysis of the Nurses Health Study, regular use of Aspirin (325 mg) twice or more per week was shown to reduce the incidence of colorectal cancers that over express Cox-2 but not the incidence of cancers with weak or absent expression of Cox-2.

In the *polyp prevention* study by Baron J A et al, a lower dose (81 mg) of Aspirin appeared to be at least equally as effective as an intermediate dose (325 mg) in preventing recurrence of polyps³⁶. In addition, dose escalation studies in normal human subjects using *mucosal PGE2 as a biomarker* have suggested that 81 mg Aspirin dose was sufficient to significantly suppress rectal mucosal PGE2 levels and did so to an equivalent extent as higher doses^{70,71}.

In both the CALGB 89803 analysis³⁰, and the study by Chan et al,³¹ the majority of participants were taking Aspirin at 325 mg per day (personal communication, [name] and [name]). In contrast, subjects in the studies by Bastiaannet et al and McCowen et al utilized low-dose aspirin (75mg to 80mg).^{32,33}

Our study uses a 200 mg daily dose, which falls directly in the middle of the dose range used by patients in the various cohort studies. We believe this intermediate dose will most optimally define the trade-off between efficacy and tolerability.

2. STUDY OBJECTIVE

To assess the effectiveness of Aspirin against placebo control in patients with dukes C or high risk dukes B colorectal cancer in terms of Disease Free Survival (DFS) and Overall Survival (OS)

3. STUDY ENDPOINTS

Primary endpoints

- DFS among all eligible subjects (high risk Dukes B colon cancer, Dukes C colon cancer and rectal cancer patient sub-groups);
- DFS among patients with colon cancer (high-risk Dukes B and Dukes C colon cancer).

Secondary endpoints

- Overall survival (OS) over 5 years
- DFS and OS in
 - Chinese, Malay, Indian and other ethnic groups
 - Resected high risk Dukes B colon cancer, Dukes C colon cancer and rectal cancer sub-groups, individually
 - Compliant versus non-compliant subjects
 - PIK3CA mutated tumors (where samples are available)

Endpoint definitions

Disease recurrence is defined as any one of the followings:

1. Unequivocal radiological evidence of colorectal cancer recurrence
2. Recurrence detected by Digital rectal examination (DRE)
3. Positive histology or cytology (i.e. peritoneal or pleural cytology)
4. Colonoscopic evidence of local cancer recurrence at the previous operation site
5. Detection of a new colon or rectal primary tumour

Disease free survival is defined as the time from randomisation to the time of documentation of disease recurrence or death from any cause. If there is no disease recurrence or death by the time when a patient is last followed up, it will be censored at that time.

Overall survival is defined as the time from randomisation to the time of death from any cause. If there is no death by the time when a patient is last known to be alive, it will be censored at that time.

Compliant subject is defined as a subject who takes the study drug for more than 70% of days for the study period during which the patient is on treatment, up to the time of discontinuation.

4. TRIAL DESIGN

Dukes C colon cancer, high risk Dukes B colon cancer, Dukes B rectal cancer or Dukes C rectal cancer patients who have completed the resection of primary tumour will be treated with standard

therapy (chemotherapy ± radiotherapy). Adjuvant chemotherapy is not specified but should consist of at least 3 months of a 5FU based chemotherapy – for example, weekly 5FU/FA (Roswell Park regimen), monthly 5FU/FA (Mayo Clinic regimen), infusion of 5FU, oral capecitabine, FOLFOX or Capecitabine/Oxaliplatin regimens. Rectal cancers may additionally have adjuvant radiotherapy administered in either adjuvant or neoadjuvant fashion. During the last cycle of standard therapy, prospective patients would be invited to participate in this study. Once informed consent is taken & within 120 days of completion of the standard therapy, they would be checked for trial eligibility.

An eligible subject will be randomised to the study in 1:1 ratio to either

- Aspirin arm: 200 mg Aspirin once a day for 3 years
- Placebo arm: 200 mg matching placebo once a day for 3 years.

After randomisation, patient will have 3 monthly assessments for 3 years (month 3 to month 36) followed by 6 monthly assessments for additional 2 years (month 42 to month 60). All subjects will be approached to seek consent for survival information (DFS, OS) after 5 years post randomization will have data collected via review of medical records or by phone contact, every 12 months until, and at the last patient last visit (month 60 visit or earlier) at the site.

The purpose of 5 year follow up is to evaluate-

1. The long term survival outcomes and
2. Persistence of effect after completion of treatment.

5. ELIGIBILITY CRITERIA

5.1. Inclusion Criteria

- Male or female outpatient of ≥ 18 years of age or \geq country's legal age for adult consent
- Dukes C colon cancer, high risk Dukes B colon cancer, Dukes B rectal cancer or Dukes C rectal cancer (*see Appendix 1 for definition of High Risk Dukes B*)
- Undergone complete resection of primary tumour
- Completed standard therapy (at least 3 months of chemotherapy ± radiotherapy)
- Within 120 days of completion of standard therapy (surgery, chemotherapy ± radiotherapy)
- ECOG performance status 0 to 2
- Satisfactory haematological or biochemical functions (tests should be carried out within 8 weeks prior to randomisation): Results of clinical investigations carried out within 8 weeks prior to randomisation can be used in place of the required screening investigations. Patients with mild laboratory abnormalities can be included at the discretion by the site principal investigator, and after approval by ASCOLT Trial Management Group
 - ANC $\geq 1.0 \times 10^9/L$
 - Platelets $\geq 100 \times 10^9/L$
 - Creatinine clearance ≥ 30 mL/min

- Total bilirubin \leq 2.0 x the upper limit normal
- AST & ALT \leq 5 x the upper limit normal
- Completed the following investigations
 - Colonoscopy(or CT colonogram(within 16 months prior to randomization)
 - Imaging of abdomen (CT or CT colonogram or MRI or PET or Ultrasound) within 16 months prior to randomization
- Written informed consent

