Objectives:	Primary Endpoint: Disease Free Survival (DFS) Secondary Endpoint: Overall Survival (OS) over 5 years
Subjects and Centres:	A total of up to 1587 patients will be randomized from multinational centres.
Inclusion Criteria:	
• Male or female outpatient of ≥ 18 years of age or \geq country's legal age for adult consent• Dukes C colon cancer, high risk Dukes B colon cancer, Dukes B rectal cancer or Dukes C rectal cancer• Undergone complete resection of primary tumour• Completed standard therapy (at least 3 months of chemotherapy \pm radiotherapy)• Within 120 days of completion of standard therapy (surgery, chemotherapy \pm radiotherapy)• ECOG performance status 0 to 2• Satisfactory haematological or biochemical functions (Tests should be carried out within 8 weeks prior to randomisation:- ANC $\geq 1.0 \times 10^9/L$, Platelets $\geq 100 \times 10^9/L$, Creatinine clearance ≥ 30 mL/min, Total bilirubin ≤ 2 x the upper limit normal, AST & ALT ≤ 5 x the upper limit normal)

[figure not shown]
Exclusion Criteria

- Completed the following investigations
 - Colonoscopy(or CT colonogram(within 16 months prior to randomization)
 - Imaging of abdomen (CT or CT colonogram or MRI or PET or Ultrasound) within 16 months prior to randomization
- Written informed consent
- Pre-existing Familial adenomatous polyposis, inflammatory bowel disease or ulcerative colitis
- Active gastritis or active peptic ulcer
- History of continuous daily use of PPI more than 1 year prior to consent
- Gastrointestinal bleeding within the past one year
- Haemorrhagic diathesis (i.e. haemophilia)
- Uncontrolled hypertension (untreated systolic blood pressure > 160 mmHg, or diastolic blood pressure > 95 mmHg)
- History of recent cancers (except for colorectal cancers, non-melanoma skin cancers, basal cell carcinomas, squamous cell carcinomas) in the past 5 years
- History of stroke, coronary arterial disease, angina, or vascular disease
- Patients who are on current long term treatment (≥ 4 consecutive weeks) with Aspirin, NSAID or Cox-2 inhibitors
- History of erosive GERD or active erosive GERD on gastroscopy.
- Patient on active current treatment with antiplatelet agents (i.e. off-study Aspirin, clopidogrel, ticlopidine)
- Patient receiving current treatment with anticoagulants (i.e. warfarin, low molecular weight heparins)
- Pregnant, lactating, or not using adequate contraception
- Patient having known allergy to NSAID or Aspirin

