A recent review of trial interim data, after enrollment of at least 1140 patients and 3 year follow-up being completed in 430 patients, revealed a pooled disease free survival rate of 79% at 5 years, we subsequently recalculated the sample size to be 1587 patients (attrition rate reduced to 10%, the rest unchanged).

In analyzing the Primary Endpoint: Disease Free Survival (DFS) and Secondary Endpoint: Overall Survival (OS), logrank test will be used to compare between groups. Hazard ratio and its 95% confidence interval will be estimated. Cox model will be further performed to adjust for potential confounding factors.

Two interim analyses are scheduled. The first analysis is a safety and toxicity analysis planned to be done after 540 patients are recruited into the study or at the mid-point of the targeted recruitment period, whichever comes earlier. The second analysis will look at safety as well as DFS and OS, after 540 patients have been followed up for 3 years, or when the cohort of patients included in the first analysis have completed follow up for 3 years..

ICR02 /ASCOLT

Assessments	Screening*		Baseline	Follow-up month (+/- 1 month)			Follow-up month (+/- 1 month) After Recurrence	Follow-up month (+/- 1 month) After Early Study Drug Discontinuation and no recurrence	Post Month 60	
				3, 9, 15, 21, 27, 33	6,12, 18, 24, 30, 36	42, 48, 54, 60	3 to 60	3 to 36		
Written informed consent		x								
Demography, Tumour history, Medical history & family history			x							
Record surgical measurements,(For rectal cancer only)			x							
Adjuvant Therapy			x							
Vital signs (Body weight, BP, height), ECOG			x							
Hb	(Within 8 weeks prior to randomisation)		x		x					
Platelet count, Creatinine, Serum Bilirubin, AST, ALT	(Within 8 weeks prior to randomisation)	x								
CEA			x	x	x	x		x		
Imaging of abdomen (CT or CT colonogram or MRI or PET or Ultrasound)	To be done if not done within 16 months prior to randomization	x		x (Mth 6, 18 and 30) Optional; or frequency according to institutional practice						
Radiological examination of the Chest (including but not restricted to Chest x ray, CT thorax or PET scan)	To be done if not done within 16 months prior to randomization	x								
Colonoscopy/CT colonogram	Full colonoscopy if not done within 16 months prior to randomization	x		x (Mth 6 and 30) Optional; or frequency according to institutional practice						
AE and SAE				x	x					
Death				x	x	x	x	x	x	
Medical Events				x	x	x	x	x	x	

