Concomitant NSAIDs				x	x	x	x	x	x	
Concomitant treatment/medication				x	x					
Recurrence, Salvage Chemotherapy				x	x	x	x	x	x	

Notes:

*Screening can start after last dose of standard therapy;

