6. RANDOMISATION

Randomization will occur within 120 days of completion of standard therapy. After informed consent is signed and subject's eligibility is confirmed, the subject can be randomised in a 1:1 allocation ratio, stratified by

- Study centre
- Tumour type (Dukes C colon, high risk Dukes B colon cancer, and rectal cancer sub-groups) and
- Type of adjuvant chemotherapy received (exposed/ not exposed to oxaliplatin)

to receive either Aspirin or a matched placebo for 3 years.

Randomisation will be done via direct web randomisation: Authorized study centre personnel will randomise the patient via a password-protected internet web site. The randomisation system will then determine the treatment arm and provide the subject number to be used for the patient. The site monitor/ project coordinator will be informed immediately in the event that the web randomisation is not successful.

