11. ASSESSMENTS AND FOLLOW-UP

11.1. Screening

Within 8 Weeks prior to randomisation

- Haematology: platelet count
- Creatinine
- LFT: serum bilirubin, AST, ALT

Within 16 months prior to randomization

- Full colonoscopy(or CT colonogram).
- Imaging of abdomen (CT or CT colonogram or MRI or PET or Ultrasound)
- Radiological examination of the Chest (including but not restricted to Chest x ray, CT thorax or PET scan)

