3.4 Assessment Schedule

The table below gives an overview of study follow-up and assessment schedule. Phone assessments are allowed at alternate 3-monthly assessments should the subject is unable to return for a follow-up. In the first 3 years, subjects with early treatment discontinuation but without recurrence will only continue with 3-monthly visit. Haemoglobin assessment will not be required for these subjects. In the first 3 years, subjects with recurrence will be assessed at 6-monthly intervals in the clinic or via phone assessments if they are unable to return for 3-monthly clinic follow up. Haemoglobin, CEA and concomitant medication assessments are not required after recurrence. In the last 2 years, subjects with recurrence may have their 6-monthly assessments via phone should they are unable to return for clinical follow up. CEA assessments are not part of these subjects' 6-monthly assessments.

Assessments	Screening*	Baseline	Follow-up month (+/- 1 month)			Follow-up month (+/- 1 month) after recurrence	Follow-up month (+/- 1 month) after early treatment discontinuation but without recurrence	Post month (
			3-monthly in first 3 years		6-monthly in last 2 years			
			3, 9, 15, 21, 27, 33	6, 12, 18, 24, 30, 36				
Written informed consent	x							
Demography, colorectal cancer surgery and tumour history, risk factors, medical history, family history of colorectal cancer		x			3-monthly followed by 6 monthly 3 to 60	3-monthly 3 to 36		
Record surgical measurements (for rectal cancer only) and synchronous tumours characteristics		x						
Adjuvant therapy		x						
Vital signs (body weight, height, blood								

pressure), ECOG																									
Haemoglobin				x											x										
Laboratory investigations (platelet count, creatinine, serum bilirubin, AST, ALT)			x (Within 8 weeks prior to randomisation)																						
CEA			x (Within 8 weeks prior to randomisation)												x										
Imaging of abdomen (CT or CT colonogram or MRI or PET or Ultrasound)			x (Within 16 months prior to randomisation)																						
Radiological examination of the chest (including but not restricted to chest X-ray, CT thorax or PET scan)			x (Within 16 months prior to randomisation)																						
Colonoscopy / CT colonogram			x (Within 16 months prior to randomisation)																						
Protocol treatment compliance															x										
Adverse event and serious adverse event															x										

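### On the wording of Protocol 5.1, a platelet count taken before the last chemotherapy dose can qualify an early entrant, and the schedule footnote does not clearly prevent it

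*Protocol*

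**What the plan says.** Protocol 5.1 sets a platelet threshold of at least 100 × 10^9/L and counts the test window back from randomisation. It then allows substitution: "Results of clinical investigations carried out within 8 weeks prior to randomisation can be used in place of the required screening investigations". SAP 1.1 carries the same sentence. The Protocol Summary gives the window alone: "Tests should be carried out within 8 weeks prior to randomisation".

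Entry has an upper limit only. Protocol section 6 states: "Randomization will occur within 120 days of completion of standard therapy". Neither 5.1 nor section 6 gives a minimum interval after chemotherapy, and section 4 has patients invited during their last cycle of treatment, so early entry is foreseen.

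Two other places bear on timing. The note under the Summary schedule and Appendix 3 reads "Screening can start after last dose of standard therapy". Section 4 says that, after consent and "within 120 days of completion of the standard therapy, they would be checked for trial eligibility".

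The platelet count appears once. Section 11.1 lists it at screening ("Haematology: platelet count"). The Summary schedule and Appendix 3 mark the row "Platelet count, Creatinine, Serum Bilirubin, AST, ALT" in the screening column only. Under 11.3 the follow-up visits schedule haemoglobin, from month 6, but no platelets.

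**The concern.** The protocol's own reasoning makes the timing of this count matter. Section 1.4 gives chemotherapy-induced thrombocytopenia as the reason aspirin cannot be given alongside chemotherapy, and section 1.2 names thrombocytopenia as a continuing problem with oxaliplatin. The screening count is the one scheduled check that the risk has passed before aspirin starts. A count taken before the final dose cannot show what that dose did.

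If such a count is accepted, a low value after the final dose would go unseen. It would not reach the Trial Management Group, which under 5.1 must approve entry with mild laboratory abnormalities. Later safeguards act on other signals. The 9.2 table responds to symptoms, bleeding or a fall in haemoglobin and has no platelet entry. Section 13.1 does not count toxicities of adjuvant chemotherapy as adverse events, so a residual low count might not be reported as one.

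The stake is bleeding risk in the aspirin arm, about half of any affected patients under 1:1 allocation.

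**Working it through.** The plan states no figure to reproduce. The check is date arithmetic plus a comparison of wordings.

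**Inputs**
- Look-back window: 8 weeks = 56 days before randomisation (Protocol 5.1, 11.1; SAP 1.1).
- Interval g from last chemotherapy dose to randomisation: no minimum stated; randomisation at most 120 days after completing standard therapy (Protocol 5.1, 6).
- Next scheduled blood-count item: haemoglobin at month 6, ± 1 month (Protocol 11.3).

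**Formulas**
- The oldest acceptable sample is 56 days before randomisation. The last dose is g days before randomisation. The sample can therefore precede the dose by max(0, 56 − g) days.
- If the sample must also follow the last dose, the usable look-back becomes min(56, g) days.

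| g (days) | Greatest lead of count over last dose (days) | Look-back if count must follow last dose (days) |
|---|---|---|
| 0 | 56 | 0 |
| 7 | 49 | 7 |
| 14 | 42 | 14 |
| 28 | 28 | 28 |
| 42 | 14 | 42 |
| 55 | 1 | 55 |
| 56 or more | 0 | 56 (unchanged) |

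The row g = 0 is a boundary; nothing suggests that patients are randomised on the day of their last dose. Where radiotherapy follows chemotherapy, g is longer and the lead shrinks or disappears.

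**Later detection.** Haemoglobin is next due at 6 − 1 = 5 to 6 + 1 = 7 months. Platelets are not scheduled again.

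**Do the other texts close the gap?**
- The footnote fixes when screening may begin. The 5.1 sentence concerns results used instead of screening tests. Nothing says whether a substitute inherits the start point of screening.
- Section 4 dates the eligibility check, not the blood sample. A check made after chemotherapy can rely on an earlier sample.

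The footnote and 5.1 therefore pull in different directions, and the documents do not say which prevails.

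**The case against.** The best counter-argument is the ordinary reading of the schedule. Platelets sit in the screening column, whose footnote starts screening after the last dose of standard therapy. On that view the 5.1 sentence only spares a patient a duplicate test during screening. This has force. A reader might infer that the protocol plainly authorises counts taken before the last dose, and the documents do not support that: the position is a conflict between two texts. What remains is that a site using a count from before the last dose could point to the words of 5.1.

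A second objection is that no harm is shown. The frequencies of early entry, of substitution and of low counts are not given. Section 1.4 concerns aspirin given with chemotherapy, whereas this trial starts it afterwards, and section 4 permits regimens without oxaliplatin. That stands, and no number of patients can be claimed.

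Third, clinical safeguards exist: the bleeding exclusions in 5.2, investigator judgement under 9.2 and 9.3, site responsibility for safety in section 13 and annual DMC safety review. They reduce the risk, but none requires a platelet count before the first tablet.

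Finally, a reader might add the 2 weeks allowed before study drug starts (9.1) to the 56 days and take 70 days as the size of the problem. That sum applies equally to patients with g of 56 or more, whose count already follows chemotherapy, so it does not measure this gap.

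**Conclusion.** The point holds as a conflict in wording with a safety consequence. On the words of 5.1 and SAP 1.1, a count up to 56 − g days older than the last chemotherapy dose can qualify a patient when g is under 56, and no later scheduled platelet count would reveal a fall. From g = 56 there is no gap.

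This assumes that a substituted result is not bound by the footnote, which the documents leave open, and that g runs from the last chemotherapy dose even where radiotherapy came later.

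The weight is that of a minor, cheap safety improvement. The documents support no claim that patients were harmed, and the analysis of DFS, type I error and power are untouched. The value of acting also depends on recruitment. The Protocol expected the last patient by the end of 2020. SAP 4.9 sets last patient last visit at 31 March 2023 with at least 1 year of follow-up, which implies entry by about 31 March 2022. If recruitment has closed, nothing remains to change.

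**What to change.** For patients still to be randomised, state in Protocol 5.1 and SAP 1.1 that the qualifying platelet count, including any clinical result used in place of the screening test, must be taken after the last chemotherapy dose and within 8 weeks before randomisation.

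That condition alone would accept a sample from the next day, which need not show the effect of the dose. For early entrants, add that the count be taken late enough to reflect it: for example, no earlier than when the pre-treatment count for a next cycle would have been due, or at the randomisation/baseline visit. The first option is safer for anyone randomised within days of the last dose, and tying it to the cycle suits the range of regimens in section 4.

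Make matching edits in the Summary inclusion criteria, the Summary schedule, Protocol 11.1, Appendix 3 and the SAP 3.4 schedule: 2 + 5 = 7 places. At randomisation, check the platelet sample date against the last chemotherapy date.

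The cost is a repeat routine blood count for some early entrants, possibly a short delay for those entering very soon after the last dose, and an amendment with ethics review at each centre (section 17), which can be bundled with the next one. The 120-day limit stays, and patients with g of 56 or more are unaffected.
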